10.1.2. Efficacy Assessments during the Study Period Postdiscontinuation Follow-Up

Postdiscontinuation follow-up during the study period will be conducted as described in the Study Schedule ([Attachment 1](#)).

For those patients who are randomized and never receive study treatment or those who discontinue study treatment without objectively measured PD, the investigative sites will continue to monitor patients and periodically evaluate tumor response approximately every 8 weeks for the first 12 months following randomization and thereafter approximately every 12 weeks by the same method used at baseline and throughout the study until the patient has objective disease progression, or until the final analysis of PFS. After the patient has objective disease progression, radiologic tests are no longer required and the patient will be followed up approximately every 12 weeks (\pm 14 days) until the patient's death or overall study completion.

Lilly will continue to collect survival data on all patients but may reduce data collection for other efficacy data. Lilly will notify investigators when this reduced data collection can begin.

10.1.3. Primary Efficacy Measure

The primary efficacy measure is progression-free survival as defined by RECIST Version 1.1 (Eisenhauer et al. 2009) provided in [Attachment 5](#).

Lilly or its designee will collect and store all tumor measurement images on all enrolled patients throughout the study. An independent review of imaging scans will be performed by an independent panel of radiologists.

The PFS time is measured from the date of randomization to the date of objective progression or the date of death due to any cause, whichever is earlier.

For those patients with nonmeasurable, bone only disease (refer to Inclusion Criterion [5]), objective progression will be established if at least 1 of the following criteria is met:

- the appearance of 1 or more new lesions (in bone or outside of bone), or
- unequivocal progression of existing bone lesions.

Pathologic fracture, new compression fracture, or complications of bone metastases will not be considered as evidence of disease progression, unless at least 1 of the above criteria is met.

For those patients with locally advanced disease for whom surgery is performed with no evidence of residual disease post-operatively, objective progression will be established if at least 1 of the following criteria is met:

- local recurrence, or
- new development of metastatic disease.

For those patients with locally advanced disease for whom surgery is performed with evidence of residual disease post-operatively, new baseline measurements should be taken and RECIST applied.

If a patient is not known to have progressed or died at the time of analysis, PFS time will be censored at the last known progression-free assessment. See Section 12.2.7 for detailed censoring rules.

10.1.4. Secondary Efficacy Measures

The following secondary efficacy measures (Table JPBL.10.1) will be collected at the times shown in the Study Schedule (Attachment 1).

Table JPBL.10.1. Secondary Efficacy Endpoints

Endpoint	Definition
Overall Survival (OS)	The time from the date of randomization to the date of death from any cause
Objective Response Rate	The proportion of patients with CR or PR according to RECIST v1.1
Disease Control Rate (DCR)	The proportion of patients with CR, PR, or SD according to RECIST v1.1
Duration of Response (DoR)	The time from the date of first evidence of a confirmed CR or PR to the date of objective progression or death from any cause, whichever is earlier
Clinical Benefit Rate (CBR)	The proportion of patients with CR, PR, or SD \geq 6 months according to RECIST v1.1

Abbreviations: CR = complete response; PR = partial response; RECIST = Response Evaluation Criteria in Solid Tumors; SD = stable disease.

Overall Survival (OS): OS duration is measured from the date of randomization of any study drug to the date of death from any cause. For each patient who is not known to have died as of the data-inclusion cutoff date for a particular analysis, OS will be censored for that analysis at the date of last contact prior to the data inclusion cutoff date (contacts considered in the determination of last contact date include AE date, lesion assessment date, visit date, and last known alive date).

Objective Response Rate: The objective response rate is the percentage of patients with a best response of CR or PR.

Duration of Response (DoR): The DoR time is defined only for responders (patients with a confirmed CR or PR). It is measured from the date of first evidence of CR or PR to the date of objective progression or the date of death due to any cause, whichever is earlier. For clarity, the start date should be determined by the initial assessment of CR or PR, not the date of confirmation of CR or PR. If a responder is not known to have died or have objective progression as of the data inclusion cutoff date scores, duration of response will be censored at the last complete objective progression-free disease assessment date.

Disease Control Rate (DCR): The DCR is the percentage of patients with a best response of CR, PR, or SD.

Clinical Benefit Rate (CBR): The CBR is the percentage of patients with a best response of CR or PR, or SD for at least 6 months.

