- [3] have postmenopausal status due to either surgical/natural menopause or ovarian suppression (initiated at least 28 days prior to Day 1 of Cycle 1) with a gonadotropin-releasing hormone (GnRH) agonist such as goserelin. Postmenopausal status due to surgical/natural menopause requires at least 1 of the following:
- prior bilateral oophorectomy
 - age ≥ 60 years
 - age < 60 years and amenorrheic for at least 12 months (in the absence of chemotherapy, tamoxifen, toremifene, or ovarian suppression) and follicle-stimulating hormone (FSH) and estradiol levels in the postmenopausal range
- [4] have a negative serum pregnancy test at baseline (within 14 days prior to randomization) and agree to use medically approved precautions to prevent pregnancy during the study and for 12 weeks following the last dose of abemaciclib if postmenopausal status is due to ovarian suppression with a GnRH agonist
- [5] have either measurable disease or nonmeasurable bone only disease. Measurable and nonmeasurable disease are defined according to the Response Evaluation Criteria in Solid Tumors (RECIST Version 1.1 [v1.1], Eisenhauer et al. 2009; refer to [Attachment 5](#)). Nonmeasurable bone only disease may include any of the following: blastic bone lesions, lytic bone lesions without a measurable soft tissue component, or mixed lytic-blastic bone lesions without a measurable soft tissue component.
- [6] are female and ≥ 18 years of age
- [7] have given written informed consent prior to any study-specific procedures
- [8] have adequate organ function, including:
- hematologic: absolute neutrophil count $\geq 1.5 \times 10^9/L$, platelets $\geq 100 \times 10^9/L$, and hemoglobin ≥ 8 g/dL. Patients may receive erythrocyte transfusions to achieve this hemoglobin level at the discretion of the investigator; however, initial study drug treatment must not begin earlier than the day after the erythrocyte transfusion.
 - hepatic: bilirubin ≤ 1.5 times upper limit of normal (ULN) and alanine aminotransferase (ALT) ≤ 3.0 times ULN
 - renal: serum creatinine ≤ 1.5 times ULN
- [9] have a performance status ≤ 1 on the ECOG scale

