12.2.8.2. Objective Response Rate, DCR, CBR, and DoR

The objective response rate, DCR, and CBR of each treatment arm will be calculated as defined in Section 10.1.4 using the ITT population. All rates will be compared between treatment arms based on a normal approximation for the difference between the rates.

The DoR time is defined only for responders (patients with a best response of CR or PR). It is measured from the date of first evidence of CR or PR to the date of objective progression or the date of death due to any cause, whichever is earlier. A Kaplan-Meier analysis of DoR will be performed to estimate the DoR curve for each arm.

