Progressive Disease (PD): At least a 20% increase in the sum of the diameters of target lesions, taking as reference the smallest sum on study (including the baseline sum if that is the smallest). In addition to the relative increase of 20%, the sum must also demonstrate an absolute increase of at least 5 mm. The appearance of 1 or more new lesions is also considered progression.

For equivocal findings of progression (for example, very small and uncertain new lesions; cystic changes or necrosis in existing lesions), treatment may continue until the next scheduled assessment. If at the next scheduled assessment, progression is confirmed, the date of progression should be the earlier date when progression was suspected.

Stable Disease (SD): Neither sufficient shrinkage to qualify for PR nor sufficient increase to qualify for PD, taking as reference the smallest sum diameters while on study.

Not Evaluable: When an incomplete radiologic assessment of target lesions is performed or there is a change in the method of measurement from baseline that impacts the ability to make a reliable evaluation of response.

Evaluation of Nontarget Lesions

Complete Response: Disappearance of all nontarget lesions and normalization of tumor marker level. All lymph nodes must be non-pathological or normal in size (<10 mm short axis).

Non-CR/ non-PD: Persistence of 1 or more nontarget lesions and/or maintenance of tumor marker level above the normal limits.

Progressive Disease: Unequivocal progression of existing nontarget lesions. The appearance of 1 or more new lesions is also considered progression.

Not Evaluable: When a change in method of measurement from baseline occurs and impacts the ability to make a reliable evaluation of response.

Evaluation of Best Overall Response

The best overall response is the best response recorded from the start of the study treatment until the earliest of objective progression or start of new anticancer therapy, taking into account any requirement for confirmation. The patient's best overall response assignment will depend on the findings of both target and nontarget disease and will also take into consideration the appearance of new lesions. The Best Overall Response will be calculated via an algorithm using the assessment responses provided by the investigator over the course of the trial.

Time Point Response

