It is assumed that at each protocol-specified time point, a response assessment occurs. (When no imaging/measurement is done at all at a particular time point, the patient is not evaluable (NE) at that time point.) Table 1 provides a summary of the overall response status calculation at each time point for patients who have *measurable disease* at baseline.

Table 1. Time Point Response: Patients with Target (\pm Nontarget) Disease

Target Lesions	Non-Target Lesions	New Lesions	Overall Response
CR	CR	No	CR
CR	Non-CR/non-PD	No	PR
CR	Not evaluated	No	PR
PR	Non-PD or not all evaluated	No	PR
SD	Non-PD or not all evaluated	No	SD
Not all evaluated	Non-PD	No	NE
PD	Any	Yes or No	PD
Any	PD	Yes or No	PD
Any	Any	Yes	PD

Abbreviations: CR = complete response; PR = partial response; SD = stable disease.; PD = progressive disease; NE = inevaluable.

Table 2 is to be used when patients have *nonmeasurable* disease only.

Table 2. Time Point Response: Patients with Nontarget Disease Only

Nontarget Lesions	New Lesions	Overall Response
CR	No	CR
Non-CR/non-PD	No	Non-CR/non-PD ^a
Not all evaluated	No	NE
Unequivocal PD	Yes or No	PD
Any	Yes	PD

Abbreviations: CR = complete response; PD = progressive disease; NE = inevaluable.

^a non-CR/non-PD is preferred over SD for nontarget disease.

Frequency of Tumor Re-Evaluation

A baseline tumor evaluation must be performed within 4 weeks before patient begins study treatment. Frequency of tumor re-evaluation while on and adapted to treatment should be protocol-specific and adapted to the type and schedule of treatment. In the context of Phase 2 studies where the beneficial effect therapy is not known, follow-up every 6-8 weeks is reasonable. Normally, all target and non-target sites are evaluated at each assessment using the same method. However, bone scans may need to be repeated only when CR is identified in target disease or when progression in bone is suspected.

Confirmatory Measurement/Duration of Response

Confirmation:

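### Do the disease control and clinical benefit rates leave out stable patients with nonmeasurable bone-only disease?

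*Protocol*

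**What the plan says.** Inclusion Criterion 5 (Protocol Section 7.1) admits patients who "have either measurable disease or nonmeasurable bone only disease". Section 10.1.4 then defines the two rates. For the first: "The DCR is the percentage of patients with a best response of CR, PR, or SD". The CBR counts CR, PR, or SD that lasts at least 6 months. Section 12.2.8.2 fixes the denominator and the test: "The objective response rate, DCR, and CBR of each treatment arm will be calculated as defined in Section 10.1.4 using the ITT population", and "All rates will be compared between treatment arms based on a normal approximation for the difference between the rates".

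Attachment 5 defines SD under target lesions only: "Neither sufficient shrinkage to qualify for PR nor sufficient increase to qualify for PD, taking as reference the smallest sum diameters while on study". For patients with nontarget disease only, its Table 2 offers CR, non-CR/non-PD, not evaluable and PD. A footnote to that table adds "non-CR/non-PD is preferred over SD for nontarget disease". On the derivation, the attachment says: "The Best Overall Response will be calculated via an algorithm using the assessment responses provided by the investigator".

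Section 10.1.3 does contain a rule for this group, but it concerns progression: "For those patients with nonmeasurable, bone only disease (refer to Inclusion Criterion [5]), objective progression will be established" by new lesions or by unequivocal progression of existing bone lesions.

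On duration of response (DoR), Section 10.1.4 and Table JPBL.10.1 require a confirmed CR or PR. Section 12.2.8.2 requires only a CR or PR as best response. The general RECIST text in Attachment 5 says that randomized trials need no confirmation.

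**The concern.** Taken word for word, a bone-only patient who stays stable has no category that reaches either numerator, although she stays in the denominator. Only a nontarget CR would rescue her. The omission stands out because Section 10.1.3 takes care to give the same patients their own progression rule, and because bone-only metastases is a level of a stratification factor, so the group was foreseen.

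If the rates were programmed that way, both arms' DCR and CBR would be understated and the difference between arms would shrink. These are listed secondary endpoints, compared at a 2-sided 0.05 level under Section 12.2.2, so a nominal result could change.

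The DoR wording raises a smaller worry. If confirmation is required for DoR but not for the response rate, the patients in the DoR curve are not the same set as the responders in the rate.

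**Working it through.** The plan states no expected DCR or CBR and no bone-only share, so there is no design figure to reproduce. The check has four parts.

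**1. What the footnote implies.** A preference for one label over another makes sense only if both could describe the same state. Table JPBL.10.1 ties DCR and CBR to RECIST v1.1, the criteria set out in the attachment that carries this footnote. The natural reading is a choice of name, not a ruling that stable bone-only disease is lack of disease control.

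**2. What the sponsor's own figures show.** Section 5.1.1 gives, for the 19 patients in Part G of the phase 1 study, 4 partial responses, a response rate of 21.1% (36.4% of the 11 with measurable disease), a DCR of 78.9% and a CBR of 63.2%.
- 4/19 = 21.1% and 4/11 = 36.4%, so all 4 responses lie in the 11 measurable patients.
- 15/19 = 78.9% and 12/19 = 63.2%.
- If only measurable patients could count, neither rate could exceed 11/19 = 57.9%.
- So at least 15 − 11 = 4 of the 19 − 11 = 8 other patients were credited with disease control, and at least 12 − 11 = 1 with clinical benefit, none of them through a response.

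**3. Whether an analyst has what is needed.**
- For CBR, Attachment 5 starts the stable-disease clock at randomization and stops it at objective progression. Section 10.1.3 defines progression for bone-only patients, so both ends of the interval exist.
- Attachment 5 also asks that SD be seen at least 6 weeks (42 days) after randomization. The first scheduled scan is at Cycle 3 Day 1, two 28-day cycles or 56 days after the first dose, and may be 3 days early: 56 − 3 = 53 days, which exceeds 42. The minimum can matter only for unscheduled scans.

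**4. What the literal reading would cost.** Let *b* be the nonmeasurable bone-only share, assumed equal in both arms, with the same rate across disease types within an arm and no nontarget CR. Then literal rate = true rate × (1 − *b*), and the arm difference shrinks by the same factor. Taking 78.9% from Part G as the true DCR and 630 patients:

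| Assumed *b* | Bone-only patients | Literal DCR | Patients with disease control not counted |
|---|---|---|---|
| 10% | 63 | 71.0% | 50 |
| 20% | 126 | 63.1% | 99 |
| 30% | 189 | 55.2% | 149 |

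**DoR.** Attachment 5 says best overall response takes account of any requirement for confirmation. If the word confirmed in Section 10.1.4 is such a requirement, the two DoR descriptions pick out the same patients. If it is not, the DoR set is a subset of the responders. The documents give no figure from which to size the difference.

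**The case for a change.** The strongest case for acting is that the gap is real on the page. Section 12.2.8.2 sends the reader to Section 10.1.4, which lacks the mapping, and a naming preference is not a counting rule. A wrong choice could also alter a nominal result. With 420 and 210 patients, rates of 70% and 60%, and an unpooled two-proportion test:
- All patients counted: standard error = √(0.70 × 0.30/420 + 0.60 × 0.40/210) = 0.0405, z = 0.10/0.0405 = 2.47, p = 0.014.
- Literal rule with *b* = 20% (56% against 48%): z = 0.08/0.0421 = 1.90, p = 0.058.

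The arithmetic stands, but it needs an assumed share, assumed rates and a reading that the footnote and Part G both speak against. It also needs the true gap to fall in a narrow band. At 70% against 65% the result is non-significant either way, and at 70% against 55% it is significant either way, for any share up to 30%.

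The Part G evidence has limits too. Its response rules are not supplied, and its 8 patients without measurable disease are not said to be bone-only. It supports the intended reading without proving it.

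On DoR, the wording mismatch between Sections 10.1.4 and 12.2.8.2 stands. Section 12.2.8.2 plans only a Kaplan-Meier curve per arm for this endpoint.

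**Conclusion.** No change to the plan is called for. This is a missing line of detail that an analyst would fill in the obvious way: non-CR/non-PD counts with SD for DCR and, if it lasts 6 months, for CBR. The only SAP text supplied is the addendum on overall survival, which refers to a main SAP (v4). Section 12.2.2 allows the SAP to hold clarifications of method. The supplied documents therefore cannot show that the mapping is absent from the plan as a whole.

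The size is bounded. Under the improbable literal reading, the rates and their difference would fall by the bone-only share, 10 to 30% on the range assumed here. If the effect is the same across disease types, the error would work against abemaciclib. Stratification by nature of disease should keep the arms similar on this factor. PFS and OS do not use these categories, and the supplied testing hierarchy runs from PFS to OS only.

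The addendum lists a data cut-off of 05May2017 after the final PFS analysis, so these rates may already have been produced. In that case new wording could only record what was programmed. The DoR discrepancy is a clerical inconsistency that affects a descriptive estimate.

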10.1.5. Exploratory Efficacy Measures

Table JPBL.10.2. Exploratory Efficacy Endpoints

Time to Progression of Bone Metastases	The time from the date of randomization to the date of earliest development of new bone metastases
Time to Worsening ECOG PS	The time from the date of randomization to the date of first PS ≥ 2
Time to First Skeletal-Related Event (TTFSRE)	The time from the date of randomization to the date of first: Spinal cord compression OR Pathological fracture OR Radiation to bone OR Surgery to bone

Abbreviations: ECOG = Eastern Cooperative Oncology Group; PS = performance status.

Time to First Skeletal-Related Event (TTFSRE): Patients will be monitored for development of SREs at each cycle. An SRE will be defined as any of the following: spinal cord compression, pathological fracture, radiation to bone, or surgery to bone. The anatomic location, days of hospitalization, relatedness to breast cancer, and procedure(s) used for treatment will be captured. Bone survey will be monitored according to the Study Schedule ([Attachment 1](#)).

TTFSRE and a comparison of the frequency of SREs between treatments will be conducted at the end of the study. TTFRSE is defined as the time from randomization to documentation of the first postbaseline occurrence of any SRE. Patients not known to have had an SRE at the time of the analysis will be censored at the date of their last complete documented assessment for SRE.

SRE-specific information should be collected until patient death, loss to follow-up, or study completion.

Time to Worsening ECOG PS: will be defined as the time from randomization to an ECOG PS evaluation of 2 or worse. Patients with no evaluation of 2 or worse will have their time to deterioration of PS censored at the date of the last PS evaluation.

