12.2.12.6. Exploratory Analyses

Joint modeling may be explored to characterize the relationship between features of the longitudinal PRO trajectories (individual items or composite scores) and the event times.

Time from randomization to earliest development of new bone metastases may be analyzed and compared between arms.

Proportion of patients who experience a "worst pain" increase of ≥ 2 points at any post-baseline visit (on or after Day 1 Cycle 2) will be compared between treatment arms. Changes in analgesic and bone agent use will be collected and summarized by arms.

Time from randomization to documentation of the first occurrence of any SRE will be evaluated. Patients not known to have had an SRE at the time of the analysis will be censored at the date of their last complete documented assessment for SRE. A log-rank test will be used to evaluate the difference of time to first SRE between treatments. Impact of other factors, including whether a

patient had at least 1 SRE prior to randomization as well as those factors used to stratify treatment randomization, will be explored.

Time from randomization to documentation of the first occurrence of any PS of ≥ 2 will be evaluated. Log-rank test will be used to evaluate the difference of time to worsening in ECOG PS between treatments.

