Attachment 1. Protocol JPBL Study Schedule

Study Schedule, Protocol I3Y-MC-JPBL

Perform procedure as indicated.

			Baseline		Patients on Study Treatment				Postdiscontinuation Follow-Up	
			BL		1	2 – 3	4 and Beyond (if Applicable)	Short-Term Follow-Up ^a	Long-Term Follow-Up ^a	
		Visit	0		1	2 – 3	4 and Beyond (if Applicable)	801	802 - 8XX	
		Approximate Duration (days)	28		28	28	28	30±5	Variable	
		Relative day within a cycle	≤28	≤14	1	15±3	1 ^p	1 ^p		
Procedure Category	Procedure	Protocol Reference								
Study Entry /Enrollment	Informed Consent Form signed ^q	Section 8.1	X ^q							
	Inclusion/Exclusion evaluation	Section 7		X						
Medical History	Medical History			X						
	Historical illnesses	Section 12.2.4		X						
	Habits assessment	Section 12.2.4		X						
Physical Examination	Height	Section 12.2.4		X						
	Weight	Section 12.2.4		X	X	X	X	X		
	Vital Signs (Temp, BP, HR, RR)	Section 12.2.4		X	X	X	X	X		
	ECOG performance status	Section 7.1 Attachment 4		X	X	X	X	X		
Tumor Assessment	Tumor measurement (palpable or visible) ^c	Section 10.1.1	X ^c			X ^c	X ^c	X ^c	X ^c	
	Radiologic imaging according to RECIST ^b	Section 10.1.1 Attachment 5	X ^b			X ^b	X ^b	X ^b	X ^b	
	Bone Scintigraphy ⁱ	Section 10.1.1 Attachment 5	X ⁱ				X ⁱ	X ⁱ	X ⁱ	
	X-ray or CT scan with bone windows or MRI ^j	Section 10.1.1 Attachment 5	X ^j			X ^j	X ^j	X ^j	X ^j	

		Baseline		Patients on Study Treatment				Postdiscontinuation Follow-Up	
		BL		1	2 – 3	4 and Beyond (if Applicable)		Short-Term Follow-Up ^a	Long-Term Follow-Up ^a
		0		1	2 – 3	4 and Beyond (if Applicable)		801	802 - 8XX
		28		28	28	28		30±5	Variable
		≤28	≤14	1	15±3	1 ^p	1 ^p		
Procedure Category	Procedure	Protocol Reference							
Survival Information ^d		Section 10.1						X ^d	X ^d
Adverse Event Collection/CTCAE Grading ^f		Section 10.3		X ^f	X ^f	X ^f	X ^f	X ^f	X ^f
Concomitant Medications (with analgesics)		Section 9.6		X	X	X	X	X	
Lab/ Diagnostic Tests	Central hematology	Attachment 2		X	X ^r	X ^r	X ^r	X ^r	
	Central serum chemistry	Attachment 2		X	X ^r	X ^r	X ^r	X ^r	
	Local FSH and estradiol levels ⁿ	Attachment 2		X ⁿ					
	Local serum pregnancy test ^o	Attachment 2		X ^o					
	Central pharmacokinetic (PK) sampling ^m	Attachment 7			X ^m	X ^m	X ^m		
	Pharmacogenetic blood sample	Section 10.4.2.2			X				
	Biomarker plasma sample	Section 10.4.2.3			X				
	Local ECG ^e	Section 10.3.2.1		X ^e	X ^e	X ^e		X ^e	X ^e
	Archived Tumor Sample ^h	Section 10.4.2.1			X ^h				

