		Baseline		Patients on Study Treatment			Postdiscontinuation Follow-Up	
		BL		1	2 – 3	4 and Beyond (if Applicable)	Short-Term Follow-Up ^a	Long-Term Follow-Up ^a
		0		1	2 – 3	4 and Beyond (if Applicable)	801	802 - 8XX
		28		28	28	28	30±5	Variable
		≤28	≤14	1	15±3	1 ^p	1 ^p	
Procedure Category	Procedure	Protocol Reference						
Study Drug	Fulvestrant Therapy ^g	Section 9.1		Days 1 and 15 of Cycle 1, then Day 1 of Cycle 2 and beyond ^g				
	Abemaciclib or Placebo Therapy ^g	Section 9.1		Q12H on Days 1 through 28 of every cycle ^g				
Health Outcomes	BPI, EORTC QLQ-C30, EORTC BR23, EQ-5D 5L ^k	Section 12.2.12		X ^k	X ^k	X ^k	X ^k	
	Skeletal-Related Events assessment ^l	Section 12.2.12		X ^l	X ^l	X ^l	X ^l	
	Hospitalization	Section 12.2.12.4		X	X	X	X	
	Transfusion	Section 12.2.12.4		X	X	X	X	

Abbreviations: BL = baseline; Temp = Temperature; BP = Blood Pressure; CT = computed tomography; CTCAE = Common Terminology Criteria for Adverse Events; ECG = electrocardiogram; ECOG = Eastern Cooperative Oncology Group; GnRH = gonadotropin-releasing hormone; HR = heart rate; IV = intravenous; PK = pharmacokinetics; MRI = magnetic resonance imaging; RECIST = Response Evaluation Criteria in Solid Tumors; RR = respiratory rate; Q12H = every 12 hours; SAE = serious adverse event; FSH = follicular stimulating hormone.

^a Short-term follow-up begins the day after the patient and the investigator agree that the patient will no longer continue study treatment and lasts approximately 30 days; the associated study procedures are performed once at the end of this period. Long-term follow-up begins the day after short-term follow-up is completed and continues until the patient’s death or overall study completion; the associated study procedures are performed approximately every 12 weeks (± 14 days) for the duration of this period.

Study Schedule, Protocol I3Y-MC-JPBL (continued)

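### Skeletal-related event collection is contradictory between Section 10.1.5 and Attachment 1, and time to ECOG PS of 2 or worse has no stated death rule and is assessed only to about 30 days after treatment

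*Protocol*

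**What the plan says.** **SREs.** Protocol Section 10.1.5 states: "SRE-specific information should be collected until patient death, loss to follow-up, or study completion". It places the analysis at the end of the study, and patients without an SRE are "censored at the date of their last complete documented assessment for SRE". In Attachment 1 the row "Skeletal-Related Events assessment" has no mark in the long-term follow-up column. Its footnote only defines the four event types and gives no timing.

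**Performance status.** Section 10.1.5 says the endpoint "will be defined as the time from randomization to an ECOG PS evaluation of 2 or worse". It continues: "Patients with no evaluation of 2 or worse will have their time to deterioration of PS censored at the date of the last PS evaluation". Death is not mentioned. Attachment 4, the scale that the schedule cites, assigns grade 5 to death. Section 12.2.12.6 adds only this: "Log-rank test will be used to evaluate the difference of time to worsening in ECOG PS between treatments". In Attachment 1 the row "ECOG performance status" is marked at baseline, during treatment and at short-term follow-up, with nothing in long-term follow-up. Footnote a says that short-term follow-up "lasts approximately 30 days; the associated study procedures are performed once at the end of this period".

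**The concern.** For SREs, two parts of the same protocol give sites different instructions. A site working from the schedule stops recording at the 30-day visit. The last documented SRE assessment then falls there, and so does the censoring date. The gap is not neutral. Radiation to bone is itself an SRE, and Section 9.6.2 requires permanent discontinuation for radiotherapy, with one exception for locally advanced disease rendered operable. A patient's first SRE can therefore coincide with leaving treatment, and later ones fall where the schedule has no SRE assessment.

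For PS, death and functional decline are closely related. Censoring a death at the preceding PS visit is unlikely to be independent of the outcome, yet the log-rank comparison assumes that it is. The objective is framed as time from randomization, but PS is collected only during treatment and for about 30 days afterwards. Treatment normally ends at progression (Section 7.3.1), so the length of the window depends on the outcome that the drug is meant to delay.

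**Working it through.** **SREs: the two texts side by side.**

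1. Section 10.1.5: collection continues to death, loss of the patient, or study completion.
2. Attachment 1: the SRE row carries four marks and an empty final cell. The questionnaire row (BPI, EORTC, EQ-5D) has the same pattern, and its footnote k runs from baseline to short-term follow-up. On that comparison the SRE row also ends at short-term follow-up.
3. Attachment 1, footnotes a and d: a long-term contact about every 12 weeks already exists, and survival information at that contact may be obtained by telephone.

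The text requires long-term collection and the schedule gives it no visit. No arithmetic is needed.

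**PS: how much of survival is under assessment.**

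Inputs:
- Control median PFS 6.5 months and hazard ratio 0.703 (Section 12.1).
- Short-term follow-up of 30 days = 30/30.4375 = 0.99 months (Attachment 1).
- Median survival of 2 to 3 years, a general figure for metastatic breast cancer (Section 5), applied equally to both arms.
- Assumptions: exponential times; treatment ends at progression.

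The plan's own figure first: 6.5/0.703 = 9.25 months, a gain of 2.75 months, and 2.75/6.5 = 42%. This matches Section 12.1.

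Share of mean survival under PS assessment = (median PFS/ln 2 + 0.99)/(median OS/ln 2).

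- Control numerator: 6.5/0.693 + 0.99 = 10.36 months.
- Abemaciclib numerator: 9.25/0.693 + 0.99 = 14.33 months.

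| Median OS (months) | Mean OS (months) | Control | Abemaciclib |
|---|---|---|---|
| 24 | 34.62 | 30% | 41% |
| 30 | 43.28 | 24% | 33% |
| 36 | 51.94 | 20% | 28% |

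Using medians throughout, (median PFS + 0.99)/median OS, the unobserved share is 69% to 79% (control) and 57% to 72% (abemaciclib). It would fall below half only if median survival were under about 2 × (6.5 + 0.99) = 15 months (control) or 2 × (9.25 + 0.99) = 20.5 months (abemaciclib).

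**PS: what counting every death as grade 5 would do.** The final OS analysis is planned at 441 deaths among about 630 patients, and 441/630 = 70%. An unrestricted composite would give at least 70% of patients an event by then. Most PS ratings stop 30 days after treatment, so many of those events would be deaths long after the last rating, and the endpoint would approach OS.

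**The case against.** The strongest points on the other side are these.

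- **Silence is not a rule.** The protocol never says in terms that deaths are censored. Since Attachment 4 grades death as 5, an analyst could count it as an evaluation of 2 or worse. This stands. A reader might infer that the protocol orders deaths to be censored; the documents support only that the literal rule leads there and that the matter is unsettled.
- **The main SAP is not available.** The SAP supplied is an addendum on OS, and Section 12.2.12 defers further detail to the SAP. Version 4 may contain a death rule. This stands for PS. It does not resolve the SRE conflict, which lies inside the protocol.
- **The table is read from extracted text.** Column positions are partly inferred. The match with the questionnaire row and its footnote makes the reading sound, but it should be confirmed on the formatted page.
- **Limited collection may be deliberate.** Section 10.1.2 lets the sponsor reduce efficacy collection other than survival, and nothing provides for rating PS by telephone. This is a fair reason not to insist on long-term PS. It does not reconcile the two SRE instructions.
- **Other data help.** Deaths are captured in PFS, OS and the safety summaries. Postdiscontinuation surgery and radiotherapy are summarized under Section 12.2.5.1, which may partly cover two of the four SRE types. This lowers the stakes.
- **A PS-or-death composite would be mostly deaths.** This stands, and it would also sit badly with PFS censoring Rule 7, which does not count events after two or more missed assessments.

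**Conclusion.** The point holds as two limited findings. First, Section 10.1.5 and Attachment 1 contradict each other on how long SREs are collected. Second, time to PS of 2 or worse has no explicit death rule and, as scheduled, is an on-treatment measure covering about 20% to 41% of mean survival. That range rests on exponential times, treatment ending at progression, and a general survival figure that is not a planning value of this trial.

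A reader might infer that both endpoints miss most of the disease course. The documents do not support that for SREs: the text requires collection throughout, and losses arise only where sites follow the schedule instead. Nor do the documents give PS event rates on or after treatment. The number of PS events lost and any bias in the comparison between arms therefore cannot be estimated from them.

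Both endpoints are exploratory; Amendment (b) moved them there because few events were expected (Section 5.2). The PFS and OS conclusions are unaffected, so priority is low.

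**What to change.** **SREs.** Reconcile Section 10.1.5 with Attachment 1 by adding an SRE mark to the long-term follow-up column, asked at the existing 12-weekly contact. The cost is a schedule amendment, a form item and a small site burden.

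**PS.**
1. State how death is handled, or cite the rule if the main SAP (v4) already has one.
2. Label the endpoint as on-treatment, to 30 days after stopping.
3. Analyze death without a prior PS of 2 or worse as a competing event.
4. As a sensitivity analysis, report PS of 2 or worse, or death, within the assessment window, with the two components shown separately.

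These four steps need wording and analysis only, because deaths are already collected. The downside is a narrower claim: the result describes function while under assessment, not over the whole disease course. Long-term PS collection would widen it but is optional, and it would need a provision for rating PS outside a clinic visit.
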